5.2. RISK/BENEFIT ASSESSMENT

5.2.1. KNOWN POTENTIAL RISKS

Participants taking part in this study will be exposed to risks that are viewed as similar to those encountered in a standard clinical practice and would be deemed as having no more than a moderate risk level. The following section describes specific risks associated with undergoing phenotyping assessments, receiving study interventions, and disclosure of confidential information (i.e., breaches of confidentiality).

Risks Associated with Phenotypic Assessments

Questionnaires: Questionnaires pertaining to pain, medication use, and history of chronic low-back pain and other pertinent comorbidities will be delivered as part of the study and may be considered burdensome and repetitive. Some participants may feel minor discomfort sharing information about topics such as physical health, mental health, and substance use.

Blood Draw / Venipuncture: Collection of blood is occasionally associated with minor bruising, risk of infection, discomfort, feeling light-headed, or fainting.

Stool collection: Participants will be asked to provide a stool sample which will be used to analyze gut microbiome. Stool samples may contain germs that may cause or spread infection if proper hygiene methods are not followed.

Biomechanical Assessment: All participants will receive at least one biomechanical assessment, part of which requires the use of wearable technology to assess biomechanical factors related to chronic low-back pain. Participants might find wearable technology uncomfortable and may experience light low back muscle fatigue or soreness similar to a light workout the day following the motion assessment. Less common are short-term aggravation of existing low back symptoms; irritation, pinching, rubbing, or sticking of skin from motion harness components; piercings or other wearable materials (e.g., insulin pump) snagging during the motion testing, and loss of balance while performing the motion assessment causing a fall.

Adhesive may be used to affix wearable sensors during assessments. These adhesives may cause short-term, minor skin irritation in some patients. A subset of participants will use wearable technology continuously for seven days, which participants may find burdensome. These assessments may also cause minor physical discomfort or tiredness but are unlikely to cause long-term physical discomfort.

Imaging: All participants will undergo Magnetic Resonance Imaging (MRI) of the spine. A subset of participants may undergo MRI of the brain and an additional spine MRI utilizing magnetic resonance spectroscopy. MRI is safe for most participants but is contraindicated for certain subsets of people, such as those with certain medical devices (e.g., implanted cardiac devices, cochlear implants, or intracranial aneurism clips) or with ferrous metal in their body (e.g., wire mesh, screws). MRI is not safe for pregnant women. While MRI is safe for most participants, the procedure may cause some participants to feel emotional discomfort, anxiety, and claustrophobia. The noise of MRI requires participants to wear ear protection and may cause peripheral muscle or nerve stimulation.

Quantitative Sensory Testing (QST): QST may cause minor but temporary physical discomfort. Specifically, the manual pressure algometer and pin prick stimulus are commonly used in QST studies and will not cause tissue injury at the maximum forces applied in this study. However, these instruments may cause minor physical discomfort in the areas of testing; this discomfort is expected to resolve within minutes of test completion. Conditioned Pain Modulation (CPM) assessments using cold stimuli are also uncomfortable but will be limited in intensity and duration to prevent tissue damage. The coldwater bath component of the QST assessment is contraindicated for certain participants with uncontrolled high blood pressure, heart conditions, and a history of Raynaud's Syndrome.

Genetic Analysis & Information: The risks related to genetic analyses can be to individuals or groups. These harms include stigmatization and impact insurability for life, disability, and long-term care insurance. If stored genetic information were re-connected to a participant's identity, personal information about the participant and the participant's health and risk of disease could become known to others. This could present unknown risks.

Risks Associated with Study Interventions and Run-in Activities

Acceptance Commitment Therapy (ACT): The ACT behavioral intervention includes discussing one's pain experience with a trained therapist and may make participants feel emotionally uncomfortable. These risks are minimal and are sometimes part of the therapeutic process. To reduce the disabling effects of depression, fear or other feelings, one may need to first recognize these before identifying healthy goals for improvement. Participants will meet with an assigned therapist four times and will be able to contact them at any time by email. The therapist will thoroughly explain treatment and what to expect. They will provide ongoing support over the course of treatment and, if applicable, will monitor the participant for worsening of depression or anxiety symptoms. Study participants may also reach out to study staff with any questions or concerns throughout the course of the study.

Duloxetine: Duloxetine will be administered with daily doses ranging from 30mg to 60mg. Participants will begin with 30 mg and may increase to 60 mg after seven days, if no or only mild side effects are experienced. Participants will be warned about the most common side effects with this drug, which include nausea, vomiting, nausea, dry mouth, constipation, diarrhea, fatigue, and difficulty sleeping. All of these side effects are thought to be less common with slow gradual dose escalation, and many (especially gastrointestinal intolerance) typically get better over time. The most serious adverse effect associated with duloxetine is the increased risk of suicidality with initiation, especially in individuals under age 25. Participants on duloxetine (of all ages) will be monitored appropriately for clinical worsening, suicidality, or unusual changes in behavior. Participants reporting a history of bipolar disorder, manic episodes, or suicide attempts and participants who are currently breastfeeding will not be eligible for participation in the Duloxetine intervention.

Enhanced Self Care (ESC): The ESC intervention is an educational and self-care digital intervention. Risks are minimal.

Evidence-Based Exercise and Manual Therapy (EBEM): Manual therapy may be used to reduce pain and stiffness and improve range of motion, and exercises may be used to improve muscle strength, flexibility and endurance. Both are considered safe for the treatment of low-back pain, but side effects associated with spinal mobilization/manipulation and therapeutic exercise are common and benign. Approximately 50% of patients report local post-manipulation or exercise muscle and/or joint soreness which typically resolves within 24 hours. Participants may also receive soft-tissue mobilization, and risks associated with this procedure are considered to be mild. Mild muscle soreness at the site of soft-tissue treatment during and after treatment has been reported. Skin irritation has also been reported when massage lotions and oils were used. Exacerbation of any low-back problem is a common risk due to natural history of the condition. Education interventions may ask patients to discuss their pain experiences and the impact of their low back pain on various aspects of his or her life possibly resulting in emotional distress. EBEM is contraindicated for certain participants with uncontrolled high blood pressure or heart conditions.

Run-in: The Run-in period is comprised of informational materials delivered digitally. Risks are minimal.

Risks Associated with Confidential Information Disclosure

Despite significant protections being put in place to protect confidential participant information (e.g., protected health information (PHI)), breaches of confidentiality, while very unlikely, are possible. An example breach of confidentiality is the disclosure of a participant's protected health information to a party that is not approved to have access to that information. A breach of confidentiality will be considered as an unanticipated problem and, as such, will be reported to the IRB of record within 48 hours of the occurrence, and a remediation plan will be put in place immediately.

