Imaging: The primary established hazard associated with MR imaging is that the magnet exerts a strong force on metal objects. For this reason, metal objects are excluded from the vicinity of the magnet so that they will not become projectiles. In addition, each subject undergoes a standard screening procedure to determine whether they have any implanted materials that may pose a risk. If there is any doubt about the nature of any implanted material, the subject will not be scanned. Participants will be instructed to bring or wear clothing without metal fasteners and remove jewelry and any other metal objects from their body. Participants will wear foam earplugs or headphones to reduce the loud noises made by the scanner. Participants will be able to communicate with the examiner throughout the scan. If needed, the participant will be removed immediately from the scanner. MRI sessions will be conducted by trained personnel. Participants will be encouraged to contact the study team if they notice any unusual symptoms or untoward side effects. The investigators have extensive prior experience in the utilization of MRI for research. The MRI machine is operated within FDA guidelines so the potential for inducing peripheral nerve stimulation is low. Participants who report pregnancy will be excluded from MRI portion of the protocol.

Quantitative Sensory Testing (QST): Study personnel will be trained by the investigators to be sensitive to participant discomfort and concerns. Participants will be instructed that they can stop any QST procedure anytime that the pain or unpleasantness of the task becomes unbearable. All procedures have been thoroughly evaluated for reliability and safety, and are well tolerated by individuals with chronic pain, causing no more than temporary mild discomfort in the body regions that will be evaluated.

Genetic Analysis: Current federal law will help protect study participants from genetic discrimination in health insurance and employment.

Risk Assessment & Mitigation for Study Interventions

Participants will be screened for contraindications to any of the BEST study interventions prior to enrolling in the study. Participants who have a contraindication to a study intervention and who are

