otherwise eligible for the study will be allowed to participate in the study but will not be randomized to the intervention for which they have a contraindication. In Sections 10.1 (Acceptance Commitment Therapy), 10.2 (Duloxetine), 10.3 (Enhanced Self Care), and 10.4 (Evidence-Based Exercise and Manual Therapy) specific details regarding risk assessment and mitigation are given for each study intervention.

Participants will be advised that they should contact study staff regarding any side effects or unexpected adverse events that occur while enrolled in the study. Prior to the start of a new study intervention, participants will be informed that if they are unable to tolerate the intervention, they are permitted to cease the intervention. Specifically for duloxetine, participants will be instructed on how to safely taper off the medication. In addition, study staff will conduct a phone call assessment with all participants approximately midway into each of the two intervention periods to evaluate pain-related outcomes as well as to ascertain how well the participant is tolerating their current study intervention(s). Participants who indicate they are unable to tolerate the intervention will be safely transitioned off their current intervention but, if in intervention period one, will be allowed to be randomized to a new intervention in the second study period. Additionally, all participants will be assessed for unexpected and adverse events 4 weeks after the end of the second intervention period (i.e., after completion of all study treatment).

Acceptance Commitment Therapy: Participants will interact with their therapist at least weekly, and the therapist will provide support as well as monitor for worsening of depression or anxiety symptoms including suicidal ideation. Participants will be encouraged to contact study staff with questions or concerns throughout the course of the study.

Duloxetine: Participants on duloxetine will be monitored appropriately for clinical worsening, suicidality, or unusual changes in behavior. Participants may be referred for appropriate treatment including emergency services if required. Participation can also be discontinued if there is active suicidal ideation.

Enhanced Self Care: The ESC intervention is an educational and self-care digital intervention. Risks are minimal; therefore, no intervention-specific risk mitigation is planned.

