8. STUDY POPULATION

8.1. STUDY INCLUSION CRITERIA

To be eligible, an individual must meet all of the following inclusion criteria:

- Ability to read and understand English
- Provision of signed and dated informed consent form(s)
- Willing and able to receive study-related messages and survey links via email
- Willing and able to receive study-related phone calls
- Age 18 years old or older
- Low-back pain for at least 3 months and occurring on at least half the days in the past 6 months
- Contraindicated to no more than one of the study interventions at the time of eligibility assessment(s)
- Eligible to receive at least three of the four study interventions and willing to receive any intervention for which they are eligible
- A PEG score 4 or higher prior to the Run-in period
- Willing and able to undergo required phenotyping as defined in Section 9
- Regular reliable access to an internet-enabled device such as a smart phone, tablet, or laptop computer
- Meet Run-in period engagement eligibility criteria:
 - Completion of two Run-in study information modules prior to period 1 randomization (Visit 0)
- Low-back pain more severe than pain in other parts of the body
- Available to complete the full study protocol (approximately 9 months)

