8.3. STUDY INTERVENTION CONTRAINDICATIONS

ACT intervention contraindications

An individual who meets any of the following criteria will be excluded from being randomized to receive ACT during the study:

Currently receiving or intending to receive within the next few months any pain-specific
psychotherapy, e.g., Cognitive Behavioral Therapy, directed towards pain even if it is only a part
of the treatment, and delivered by a psychologist or social worker

Duloxetine intervention contraindications

An individual who meets any of the following criteria will be excluded from being randomized to receive duloxetine during the study:

- Pregnant: If the participant becomes pregnant during the study, duloxetine will be rapidly tapered.
- Currently taking any of the following:

Duloxetine

Lithium

Tramadol (Ultram, Ultracet)

St. John's Wort

Prochlorperazine (Compazine)

Thioridazine (a psychiatric medication)

Propafenone or Flecainide (for heart rhythm problems)

Ciprofloxacin (Cipro, an antibiotic)

Linezolid (Zyvox, an antibiotic)

Methylene Blue

Cimetidine (Tagamet, for heartburn)

Bupropion (Wellbutrin)

SNRIs:

Venlafaxine

Milnacipran

Duloxetine

Sibutramine

Atomoxetine

Desvenlafaxine

Levomilnacipran

SSRIs:

Sertraline

Paroxetine

fluoxetine

escitalopram

citalopram

fluvoxamine

Vortioxetine (Trintellix)

Any other contraindicated SNRIs, SSRIs, and antidepressants

Reporting a current or previous diagnosis of any of the following

Renal dysfunction

End-Stage Renal Failure

Hepatic dysfunction

- Previous allergic or other severe adverse reaction to duloxetine or, as determined by the site PI, a medicine with duloxetine cross-reactivity.
- History of bipolar disorder, manic episodes, or suicide attempts
- Currently breastfeeding

EBEM intervention contraindications

An individual who meets any of the following criteria will be excluded from being randomized to receive EBEM during the study:

- Currently receiving or intending to receive within the next few months any type of manual therapy or exercise treatment for low-back pain from a licensed provider
- Uncontrolled high blood pressure (≥150 systolic and/or ≥100 diastolic)
- Uncontrolled coronary artery disease
- Inability to walk at least 50 feet unassisted
- Contraindication for manual therapy
- Contraindication for participation in an exercise program

ESC intervention contraindications

An individual who becomes pregnant during the study will be counseled to stop NSAIDs.

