11. STUDY INTERVENTION DISCONTINUATION AND PARTICIPANT DISCONTINUATION/WITHDRAWAL

11.1. DISCONTINUATION OF STUDY INTERVENTION

Early discontinuation of treatment is anticipated to be rare. Examples include a broken leg, precluding continuation of EBEM, or adverse reaction to duloxetine, necessitating discontinuation of duloxetine treatment.

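### A recorded contraindication for an exercise program bars a participant from EBEM only, so ESC can still prompt that person to start unsupervised walking

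*Protocol*

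**What the plan says.** **Risk statements.** Protocol 5.2.1 disposes of ESC briefly: "The ESC intervention is an educational and self-care digital intervention. Risks are minimal". Walking is not mentioned there. Section 5.2.3 adds for ESC: "Risks are minimal; therefore, no intervention-specific risk mitigation is planned".

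**Screening and its effect.** Section 5.2.3 states: "Participants will be screened for contraindications to any of the BEST study interventions prior to enrolling in the study". A person with a contraindication who is otherwise eligible stays in the trial and "will not be randomized to the intervention for which they have a contraindication". Section 8.1 permits one contraindicated intervention and requires willingness to take any arm that remains open.

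**Contraindication lists (8.3).** The EBEM list includes "Contraindication for participation in an exercise program". The only entry under ESC is "An individual who becomes pregnant during the study will be counseled to stop NSAIDs".

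**ESC content.** The Synopsis (4.1) gives all ESC participants the same material in weeks 1 to 4. Section 10.3.1 places the Fitbit walking program in Week 3, has text or email messages direct participants to try it, and describes it as aerobic exercise. Section 10.3 says no therapist is involved.

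**The concern.** Read together, these sections let the trial record that a person should not take part in an exercise program and then send that person a message to begin one without supervision. The matter is patient safety and consistency between the eligibility and risk sections. It does not touch the sample size or the analysis.

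The protocol is more careful elsewhere. For a short, staff-supervised motion assessment, 5.2.1 discloses soreness, aggravated back symptoms and a possible fall. For the over-the-counter analgesic module of ESC, 10.3.1 says the materials will send people to their own provider when oral NSAIDs are unsuitable. No equivalent is stated for walking.

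**Working it through.** The plan gives no figure on this point, so the check is mainly a reading of the sections in sequence.

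1. *Can a person with this contraindication enroll?* Yes. It counts against EBEM alone, and 8.1 allows one.
2. *Can that person receive ESC?* Yes. Under 5.2.3 the bar covers only the contraindicated arm, and the ESC entry in 8.3 has no exercise item. The routes are Stage 1 assignment, or Stage 2 after ACT or duloxetine, by augmentation or switch (Table 10.1).
3. *Will the walking message go out?* Yes. Weeks 1 to 4 are common to all ESC participants; personalization starts after the fourth module (10.3.1).
4. *Is there a walking-specific check first?* None is stated in 5.2.1, 5.2.3, 8.3 or 10.3.1.
5. *Who is already kept out?* Section 8.4 makes inability to walk 50 feet unaided or to stand for 10 minutes a contraindication to the biomechanical assessment. Section 9 makes that assessment required and excludes anyone contraindicated to it. The gap therefore concerns other exercise contraindications in people who can walk.

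**Timing of the next scheduled contact**
- Stage 1: prompt at Week 3, call at Week 6; 6 − 3 = 3 weeks.
- Stage 2 starters, assuming the same weekly schedule: prompt at 12 + 3 = Week 15, call at Week 18; 18 − 15 = 3 weeks.

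Participants may contact staff or stop at any time in between (5.2.3).

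**Illustration of the chance of ESC, given this contraindication.** Assume equal probabilities among eligible options and no dropout. Let *m* be the share who maintain their Stage 1 arm at Week 12, which the documents do not give. Three arms are open in Stage 1. Someone who starts on ACT or duloxetine and is not maintained has two new options, one of them ESC.

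P(ESC at either stage) = 1/3 + (2/3)(1 − m)(1/2)

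| m | P |
|---|---|
| 1 | 0.33 |
| 0.5 | 0.50 |
| 0.2 | 0.60 |
| 0 | 0.67 |

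Actual probabilities may differ, because 10.4.4 uses minimization and adjusts for people eligible for only three arms. The table says nothing about how many people carry the contraindication.

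**The case against.** **The 8.3 item may mean EBEM's own exercise.** It is undefined and sits beside a manual-therapy item, in the list for an arm of clinician-delivered treatment. It is not shown to apply to self-paced walking. This has force. But the item is worded generally and stands as a separate bullet, and 10.3.1 itself calls the walking aerobic exercise. If a narrower meaning is intended, the protocol should say so.

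**Clinical judgment already covers ESC.** Section 8.2 lets the investigator exclude anyone who could not participate safely, and 12.2 requires a baseline physical assessment. These controls are real and reduce the exposure. However, 8.2 removes a person from the whole trial, whereas 8.1 deliberately keeps people with one contraindication. It cannot hold back one automated message.

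**The module may be cautious already.** Section 10.3.1 says it builds on pacing and self-care content and offers goal-setting suited to these patients. That is not stated as a safety precaution, but the module itself, the Manual of Procedures and the consent form are not available, so a warning there cannot be ruled out.

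**Stronger readings that the documents do not support.**
- A reader might infer that people unable to walk are prompted to walk. Sections 8.4 and 9 exclude them at entry.
- A reader might extend the EBEM blood-pressure and coronary criteria to ESC. They are set for EBEM as a whole, and nothing shows that they apply to self-paced walking.
- A reader might take the 11.1 example ("Examples include a broken leg, precluding continuation of EBEM") to mean that someone with a fracture would be switched to ESC and told to walk. ESC is a listed switch after EBEM. But 11.1 expects early discontinuation to be rare, Visit 1 includes tolerability and motion assessments before any Stage 2 prompt, adverse events are followed, and 11.2 lets the physician or investigator stop treatment or participation. The example shows only that a contraindication can arise after entry.

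**Conclusion.** The inconsistency is in the text and should be closed. An ambulatory participant with a recorded contraindication for an exercise program can be assigned to ESC and receive the Week 3 walking prompt with no stated walking-specific precaution.

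Its size is limited. Walking is suggested and not enforced, tolerability is assessed at Weeks 6, 12, 18 and 24, and the number affected is unknown and probably small. The documents do not show that anyone was harmed or that ESC is unsafe in general.

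The conclusion assumes that the 8.3 item carries its ordinary, general meaning and that no unavailable document already holds such a rule. Confidence is medium for those two reasons.

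**What to change.** 1. **8.3, under ESC.** State that participants with a recorded contraindication for an exercise program, whether at entry or noted at Visit 1 before ESC starts, remain eligible for ESC. The walking message is held. Because all ESC content stays open to participants, staff tell them at the ESC orientation not to start that module unless the site clinician documents clearance. Do not import the EBEM blood-pressure or coronary criteria.
2. **5.2.3, ESC paragraph.** Replace the statement that no specific mitigation is planned with this rule.
3. **5.2.1, ESC paragraph.** Name walking as a component, with foreseeable minor risks such as soreness and short-lived aggravation of back symptoms.

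If the Manual of Procedures or the module already contains the rule, cite it instead.

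**Cost.** Short protocol wording, matching consent wording if absent, and a flag so that one message is held. The documents describe no link between PainGuide and the randomization system, so site staff may have to set the flag by hand when they create the account. Contraindications are already screened before enrollment, so no new screening item is needed at entry, and eligibility and sample size are unchanged. ESC content becomes slightly less uniform for a few people, so record who was flagged. The SAP already reports randomized totals for both stages, so the change may serve only remaining or future use of the protocol.
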